## 7. PLANNED ANALYSIS

In general the display format of the analysis results follow BI guideline and standards as much as possible.

For End-Of-Text tables, the set of summary statistics is: N / Mean / Standard Deviation (STD) / Min / Median / Max.

For tables that are provided for endpoints with some extreme data, median, quartiles and percentiles are preferred to mean, standard deviation, minimum and maximum.

In general, means, medians, and percentiles are presented to one more decimal place than the raw data and STDs are presented to two more decimal places than the raw data. Minima and Maxima are presented to the same number of decimal places as the raw data.

Tabulations of frequencies for categorical data include all possible categories defined (even if there is no count in a category) and display the number of observations in a category as well as the percentage (%) relative to the number of subjects in the respective treatment group (unless otherwise specified, all subjects in the respective subject set whether they have non-missing values or not). Percentages are rounded to one decimal place. The category missing is displayed only if there are actually missing values.

If a table presents only categorical data, "[N (%)]" is displayed in the column header only.

Abbreviations (e.g. Wors.) or acronyms (e.g. PD) will not be displayed in tables and subject data listings without any explanation. They will be either spelled out or explained in footnotes.

If applicable, conversion from days to weeks, months and years will be as follows:

- weeks = days  $\div$  7
- months =  $12 \times \text{days} \div 365.25$
- years = days  $\div$  365.25.

#### 7.1 DEMOGRAPHIC AND OTHER BASELINE CHARACTERISTICS

Only standard descriptive statistics and summary tables are planned for this section of the report based on the treated set and other subject sets as appropriate. Data will be summarised by treatment group and a "total" column will be included in the summary table.

#### 7.2 CONCOMITANT DISEASES AND MEDICATION

Only descriptive statistics are planned for this section of the report based on the treated set and other subject sets as appropriate.

Concomitant diseases are coded similarly as AEs based on the most current MedDRA® version. A summary of concomitant diseases will be provided by treatment group, system organ class (SOC), and preferred term (PT).

Concomitant therapies (CTs) are coded according to WHO DD. CTs will be classified according to the Anatomical, Therapeutic, Chemical (ATC) classification system. The third ATC level will be used to categorise CTs by therapy type. In situations where a medical product may be used for more than one equally important indication, there are often several classification alternatives. As appropriate, subjects receiving CTs with more than one possible ATC level-three category will be counted more than once and footnote will clarify this possible multiple counting in tables. CTs will be summarised in two groups: psycho-active and non-psycho-active concomitant medications. CTs of special interest, e.g. antipsychotic CTs, may also be defined and explored in detail.

#### 7.3 TREATMENT COMPLIANCE

Treatment compliance is calculated at Week 3, 6, 9, and 12/EOT using the following formula:

Treatment Compliance = (number of tablets actually taken during a time period) / (number of tablets that should have been taken during a time period) \* 100.

For early discontinued subjects, if there is documented evidence for taking the subject off the drug, for example due to an adverse event, then the drug stop date should be used to derive the treatment period for treatment compliance; if there is no documented evidence for taking the subject off the drug, for example a subject came to a planned in-office visit and informed the study investigator that she/he has already stopped taking the drug several days ago because she/he did not want to continue the study, then this in-office visit is the EOT visit and the EOT visit date should be used to derive the treatment period for treatment compliance. The following is an example to illustrate the calculation of treatment compliance.

#### Scenario 1

- A subject started treatment on June 5, 2019
- This subject had an AE on June 10, 2019
- Study investigator decided to stop the trial medication for this subject on June 11, 2019
- This subject had EOT visit on June 17, 2019 for early discontinuation

Treatment Compliance for Scenario #1 = (number of tablets this subject actually took between June 5 and 11, 2019) / (number of tablets that this subject should have taken between June 5 and 11, 2019) \* 100

#### Scenario 2

- A subject started treatment on June 5, 2019
- This subject decided to stop taking the trial medication on June 10, 2019
- This subject came to office for the planned Visit 3 on June 26, 2019 per CTP flowchart, withdrew consent for continuing with this trial, and then Visit 3 became EOT visit

#### Boehringer Ingelheim TSAP for BI Trial No: 1346.9

Proprietary confidential information © 2020 Boehringer Ingelheim International GmbH or one or more of its affiliated companies

Treatment compliance for Scenario #2 = (number of tablets this subject actually took between June 5 and 26, 2019) / (number of tablets this subject should have taken between June 5 and 26, 2019) \* 100.

The cumulative treatment compliance during the entire treatment period is derived using the following formulas:

For completers: if a subject's observed treatment compliance rates are 85% at Week 3, 90% at Week 6, 100% at Week 9 and 100% at EOT, then the cumulative treatment compliance rate  $= (0.85^{*}3 + 0.90^{*}3 + 1^{*}3 + 1^{*}3)/12 * 100\% = 93.75\%$ .

*For early discontinued subject:* if a subject's observed treatment compliance rates are 85% at Week 3, 100% at Week 6, 50% at EOT visit, and this subject did not discontinue early due to AE, then the cumulative treatment compliance rate = (0.85\*3 + 1\*3 + 0.5\*((EOT date - drug start date + 1)/7 - 6))/((EOT visit date - drug start date + 1)/7) \* 100% = 85.7% if EOT visit date - drug start date + 1 = 50 days. If there is documented evidence of early discontinuation due to AE before the EOT visit date for this subject, then replace EOT visit date with the documented drug stop date in the above formula.

If any one of the by-visit treatment compliance rates is missing, then the cumulative treatment compliance should be non-evaluable.

Only descriptive statistics are planned for this section of the report. Summary statistics of compliance, by-visit and cumulative compliance, in the treated set will be given for the number of subjects as well as the corresponding percentage with compliance in the categories <80%, 80% - 100%, >100% - 120%, >120% for by-visit compliance and <80%, 80% - 100%, >100%, >100% for cumulative compliance.

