4.1.4 Drug assignment and administration of doses for each patient

Dispensing of kits for the double-blind treatment period will begin at Visit 2. Trial medication kits will be provided at Visit 2 and Visit 4. At each of these visits, medication assignment will be provided through IRT. The assigned medication number(s) must be entered in the eCRF, and the corresponding medication kit(s) must be given to the patient. The duration of treatment is 12 weeks. At both Visit 2 and Visit 4 patients will receive one treatment kit containing supplies for 42 treatment days (plus 7 day reserve).

Following the screening period, patients who qualify according to entry criteria will be randomized to one of the five treatment groups of the treatment period to be evaluated as outlined in Table 4.1.4: 1.

Boehringer Ingelheim		28 Mar 2019
BI Trial No.: 1346.9		
Doc. No.: c03559983-04	Trial Protocol	Page 36 of 116

Since the tablet size of 1mg and 5 mg is smaller than the tablets size of 25mg, the number of tablets per day will be 3 for all treatments (once daily) to maintain blinding.

Table 4.1.4: 1	Treatment administration per dose group and day (first treatment
	period)

Treatment group	Dose	Total units per daily dose
BI 425809 2mg	BI 1mg/BI 1mg /placebo 2**	3
BI 425809 5mg	BI 5mg/placebo 1*/placebo 2**	3
BI 425809 10mg	BI 5mg/BI 5mg/placebo 2**	3
BI 425809 25mg	Placebo 1*/placebo 1*/BI 25mg	3
Placebo	Placebo 1*/placebo 1*/placebo 2**	3

*placebo 1 matching BI 425809 1mg and 5mg tablets

**placebo 2 matching BI 425809 25mg tablets

Patients should be instructed to take three tablets orally with water and with or without food in the morning, except for visit days where patients will be given their daily dose at the trial site. If a dose is missed by more than 12 hours, that dose should be skipped and the next dose should be taken as scheduled. On days prior to a visit, the dose should be taken approximately 24 hours before the planned dose at the visit.

The first dose of study medication will be taken at the end of Visit 2 under supervision of the investigator or site staff. The last dose of study medication should be taken on the day before the End of Treatment visit.

Patients should be instructed not to take their trial medication in the morning before visit days, as they will be dosed at the site. Patients who fail to do so should have the visit rescheduled as soon as possible, ideally on the following day. A dose reduction of BI 425809 is not possible.

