4.3 TREATMENT COMPLIANCE

Study medication will be dispensed to the patient at the study site by responsible site personnel. Details regarding dispensing of the study medication to each participating patient, including patient identification, the amount of study drug dispensed, the date the drug was dispensed, and the numbers of tablets returned to the site will be recorded in the drug accountability log. All dispensed study drug should be recorded in the drug accountability log of the investigator site file.

Patients are requested to bring all remaining trial medication including empty package material with them when attending visits.

Based on tablet counts, treatment compliance will be calculated as the number of tablets taken, divided by the number of tablets which should have been taken according to the

Topretary connection mornation @ 2017 Deciminger ingemenn methational Ginori of one of more of its armated companies

scheduled period, multiplied by 100. Compliance will be verified by the on-site monitor authorized by the Sponsor.

Treatment compliance (%) =	Number of tablets actually taken \times 100			
	Number of tablets which should have been taken			

If the number of doses taken is not between 80-120%, site staff will explain the patient the importance of treatment compliance.

Page 42 of 116

Proprietary confidential information © 2019 Boehringer Ingelheim International GmbH or one or more of its affiliated companies

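### Cumulative compliance in SAP 7.3 uses nominal 3-week weights and is lost when one visit count is missing, so the C3.1 count and the cumulative table can be wrong or incomplete

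*SAP*

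**What the plan says.** Protocol Section 4.3 defines the measure as a ratio of counts: "treatment compliance will be calculated as the number of tablets taken", divided by the number due. SAP Section 7.3 uses the same ratio for each period ending at Week 3, 6, 9 and 12/EOT.

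For the whole treatment period, SAP Section 7.3 then combines the by-visit percentages, and defines the rule through two worked examples.

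- Completers: "if a subject's observed treatment compliance rates are 85% at Week 3, 90% at Week 6, 100% at Week 9 and 100% at EOT", each rate is multiplied by 3 weeks and the sum is divided by 12.
- Early stoppers: each visit already passed gets a nominal 3 weeks. The last interval gets the actual weeks on treatment minus those nominal weeks, and the denominator is the actual weeks. The example result is "85.7% if EOT visit date - drug start date + 1 = 50 days".

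The missing-data rule is: "If any one of the by-visit treatment compliance rates is missing, then the cumulative treatment compliance should be non-evaluable".

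The cumulative value feeds two outputs. SAP Table 6.2: 1, code C3.1, makes a value below 80% an important protocol deviation, with no exclusion from any analysis set. SAP Section 7.3 also tabulates it in categories that end ">100%, >100% for cumulative compliance", whereas the by-visit categories separate over-use at 120%.

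**The concern.** Averaging percentages with fixed weights equals a ratio of totals only when the true intervals match the weights. The protocol flow chart allows Visits 3, 4 and 5 to move by 3 days either way and Visit 6 by up to 3 days later, so they need not match. The early-stopper version mixes nominal blocks with actual days, so the last interval absorbs every departure from schedule.

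The missing-data rule discards more than it needs to. Protocol Section 4.1.4 has one kit issued at Visit 2 and one at Visit 4, and Section 6.2.2 has the first dose from the new kit taken in the clinic at Visit 4. The totals therefore need only two returns, not four counts.

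At stake are the number of patients recorded under C3.1, which is the only listed deviation for non-compliance with trial medication, and the only whole-treatment compliance summary in the SAP.

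**Working it through.** **The plan's own figures**

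- Completer: (0.85×3 + 0.90×3 + 1×3 + 1×3)/12 = 11.25/12 = 93.75%. Reproduced.
- Early stopper, 50 days: (0.85×3 + 1×3 + 0.5×(50/7 − 6))/(50/7) = 85.7%. Reproduced.

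**Inputs for the comparison**

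The protocol flow chart allows Visit 3 on Days 19–25, Visit 4 on Days 40–46, Visit 5 on Days 61–67 and Visit 6 on Days 85–88. Protocol Section 4.1.4 states "The last dose of study medication should be taken on the day before the End of Treatment visit", so a completer's dosing intervals are (V3 − 1), (V4 − V3), (V5 − V4) and (V6 − V5) days. Three tablets are due every day, so tablets taken over tablets due equals the by-visit rates weighted by actual days.

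**Completers**

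- On schedule (21/21/21/21 days): the two calculations are identical.
- The SAP's completer example, over all in-window visit days: 93.2% to 94.5% by count, against 93.75%.
- Visits on Days 25, 40, 67 and 85 (24/15/27/18 days) with rates 60/95/70/100%. SAP: (0.60 + 0.95 + 0.70 + 1.00)/4 = 81.25%. By count: (24×0.60 + 15×0.95 + 27×0.70 + 18×1.00)/84 = 65.55/84 = 78.0%. C3.1 is missed.
- Opposite direction: visits on Days 19, 46, 61 and 88 (18/27/15/27 days) with rates 50/100/50/100%. SAP: 75.0%. By count: (9 + 27 + 7.5 + 27)/87 = 70.5/87 = 81.0%. C3.1 is recorded wrongly.
- Rates kept between 80% and 100%: the largest gap comes from 80/100/80/100% on those same days. SAP: 90.0%. By count: (14.4 + 27 + 12 + 27)/87 = 80.4/87 = 92.4%. Gap: 2.4 points.

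**Early stoppers**

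Take the last interval to run from the Visit 4 day to the end date inclusive, and each visit already passed to count 3 weeks, as in the SAP's example.

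- The 50-day example with Visits 3 and 4 on Days 25 and 40 (24/15/11 days): (20.4 + 15 + 5.5)/50 = 81.8%. With Days 19 and 46 (18/27/5 days): (15.3 + 27 + 2.5)/50 = 89.6%. The SAP formula gives 85.7% in both.
- Visit 4 on Day 40, EOT on Day 41, rates 100/100/50%. Weight of the last interval: 41/7 − 6 = −0.14 weeks. SAP: (3 + 3 − 0.5×0.143)/(41/7) = 5.929/5.857 = 101.2%. By count: (39×1 + 2×0.5)/41 = 40/41 = 97.6%. The SAP value exceeds 100% although no extra tablet was taken.

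**Missing counts**

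- Three visits at 65% and the fourth missing: even a fourth rate of 120% gives (3×65 + 120)/4 = 78.75%. It would need 4×80 − 3×65 = 125% to reach 80%. The value is still declared non-evaluable, so C3.1 cannot be triggered.
- The documents give no rate of missing counts. Assume each is missing independently with probability p. Non-evaluable share of completers under the SAP is 1 − (1 − p)^4; needing only the Visit 4 and EOT returns it is 1 − (1 − p)^2.

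| p (assumed) | SAP rule | Kit returns |
|---|---|---|
| 1% | 3.9% | 2.0% |
| 3% | 11.5% | 5.9% |
| 5% | 18.5% | 9.8% |

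**The case against.** The strongest reply is that nothing inferential depends on this number. C3.1 excludes nobody, Section 7.3 is descriptive, and the per-protocol set is reduced through other codes. That stands, and it caps the importance of the point.

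It is also fair that the completer discrepancies are constructed. They need visits near opposite window limits and poor adherence in the longer or shorter intervals. Both calculations are weighted averages of the same four rates, so a completer who changes sides of 80% must have at least one by-visit rate below 80%. The by-visit table shows that rate, and it is a trigger for site counselling. Missing counts are likewise lost only from the cumulative figure. This makes the error occasional and partly visible; it does not make the formula right.

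Four stronger readings are tempting and are not supported.

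- **The SAP contradicts the protocol formula.** Protocol Section 4.3 refers to the scheduled period and defines no cumulative statistic, and the SAP keeps its ratio within each period. The fault lies in how the periods are combined.
- **Over-use should be a deviation.** The protocol instruction beginning "If the number of doses taken is not between 80-120" per cent leads to an explanation by site staff. It is not a deviation limit, so a one-sided C3.1 conflicts with nothing. Over-use is tabulated by visit, and SAP Section 6.2 allows further deviations to be added.
- **The early-stopper formula wrongly counts the EOT day.** Drug is given on site at Visits 3 to 5. When such a visit becomes the EOT visit, as in the SAP's Scenario 2, that day was a scheduled dosing day. The documents do not settle the matter.
- **The repeated >100% category shows that cumulative over-use above 120% was deliberately merged.** It may be a typing or text-extraction fault and only needs checking.

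**Conclusion.** The concern holds as a minor fault in a stated rule. The SAP formula agrees with tablets taken over tablets due for completers seen on schedule. It can differ by several points when visits are off schedule within the windows and adherence is uneven, enough to cross 80% in either direction, and it can assign an early stopper's last interval a negative weight. How often this happens cannot be derived from the documents.

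The missing-count rule is the more practical weakness: it blocks the C3.1 flag when the total is recoverable, or when the remaining counts all but settle the answer. The non-evaluable percentages rest on assumed, independent missingness. If missed visits go with missed doses, which is plausible but not shown, the lost values would not be a random subset.

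The reach is limited to the C3.1 count and the cumulative compliance table. A reader might infer that efficacy results or the per-protocol set are distorted; they are not.

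**What to change.** In SAP Section 7.3:

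- Define cumulative compliance as 100 × total tablets taken / total tablets due over the actual treatment days, keeping the SAP's existing rules for the stop date of early stoppers.
- When a Visit 3 or Visit 5 count is missing, derive the total from kit-level accountability at Visit 4 or EOT.
- Treat the value as non-evaluable only when a kit's return is not documented, and do not assume that unreturned tablets were taken.
- Report the number of patients non-evaluable beside the C3.1 count and in the cumulative table.
- Check the duplicated >100% category against the by-visit categories and correct it if it is an error.

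The cost is a short wording change and simpler programming. The data needed are the dispensing and return records that Protocol Section 4.3 already requires in the drug accountability log. No visit, assessment or analysis set changes.

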#### 7.4 PRIMARY ENDPOINT

#### 7.4.1 Primary analysis of the primary endpoint

The MCPMod approach (6, 7) is implemented in two main stages: (1) trial design stage; (2) trial analysis stage. The procedures for the trial design stage, including the selection of candidate models covering a suitable range of dose-response shapes and sample size and power calculations are provided in the CTP Section 7.3.1 and 7.7. The procedures for the trial analysis stage are specified below. FAS is used for the primary analysis of the primary efficacy endpoint.

The change from baseline in MCCB overall composite t-score at Week 12 as well as the corresponding variance-covariance matrix are estimated using a mixed effects model repeated measure (MMRM) including the fixed categorical effects of treatment, visit and treatment-by-visit interaction, as well as the fixed continuous covariates of the baseline MCCB overall composite t-score and the baseline-by-visit interaction, and subject is considered as random effect. The unstructured covariance matrix is used to estimate the within subject errors. Then the pair-wise comparison procedure will be implemented using the optimal contrast tests which control the family-wise type I error rate at one-sided  $\alpha$ =0.05. The optimal contrasts corresponding to the candidate models are calculated as in the trial design stage and shown in

#### Boehringer Ingelheim TSAP for BI Trial No: 1346.9

Proprietary confidential information © 2020 Boehringer Ingelheim International GmbH or one or more of its affiliated companies

Table 7.4.1: 1 below. These contrasts will be updated using the expected model means from the candidate set and the estimated variance-covariance matrix from the data.

	Optimal Contrast Coefficients for Dose				
Model	0	2mg	5mg	10mg	25mg
Linear	-0.593	-0.212	-0.085	0.127	0.762
Linear in log	-0.844	-0.012	0.146	0.271	0.439
Emax	-0.773	-0.142	0.083	0.292	0.539
Sigmoid Emax	-0.623	-0.295	-0.078	0.389	0.606
Logistic	-0.542	-0.254	-0.181	0.231	0.745
Beta model	-0.782	0.173	0.358	0.441	-0.190

 Table 7.4.1: 1
 Optimal contrast coefficients

Proof of concept is established if at least one dose-response model is statistically significant, i.e. the null hypothesis of a flat dose-response curve is rejected indicating a benefit of one BI 425809 dose over placebo.

Once the significance of a dose-response signal is established, the dose-response profile and the target dose can be estimated using the model averaging method. The selected dose-response model(s) is re-fitted to the data without any parameter assumptions to generate a set of new estimates of the model parameters from the data. The final dose-response model is obtained via the weighted model averaging based on Akaike Information Criterion (AIC) (the smaller the AIC value the better the model fit). Estimate of the target dose is the smallest dose producing an effect greater than or equal to the target effect size of 0.35 based on the final dose-response model as well as considering safety information and other relevant information.

The MCPMod trial analysis will be implemented by calling an R function/package within SAS.

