7.3.1 Primary endpoint analyses

7.3.1.1 Primary analysis of the primary endpoint

The analyses of PoCC and dose finding are carried out using the MCPMod approach (R10-1424) in combination with Mixed effects Model Repeated Measures (MMRM) approach (R15-4293) whereby several plausible dose response patterns/models are evaluated, while keeping full control of the overall type I error rate of 5% 1-sided, to identify the best-fitting model or subset of models. The MMRM model as specified in Section 7.3.1.2 will be fitted for the MCPMod.

For the PoCC testing and for the sample size calculation, the basic shape of each of the models to be tested must be pre-defined. Six different models are considered in the analysis: linear, linear in log, Emax, Sigmoid Emax, logistic and beta model. Except in the beta model, the maximum effect is assumed to be achieved at the maximum dose being tested. For the sample size calculation, the maximum standardized effect size is assumed to be 0.35. Further details are given in Section 7.7.

The active BI 425809 doses are 2 mg, 5 mg, 10 mg, and 25 mg once daily. The following model assumptions and resulting graphs (Figure 7.3.1.1: 1) have been selected to cover both plausible and a diverse range of dose response patterns:

- Linear: no assumptions needed
- Linear in log: no assumptions needed
- Emax: 20% of the maximum effect is achieved at 2 mg
 Sigmoid Emax: 25% of the maximum effect is achieved at 5 mg 75% of the maximum effect is achieved at 10 mg
 Logistic: 10% of the maximum effect is achieved at 5 mg 50% of the maximum effect is achieved at 10 mg
 Beta model: 75% of the maximum effect is achieved at 2 mg 87.5% of the maximum effect is achieved at 5 mg 25% of the maximum effect is achieved at 2 mg Maximum effect achieved at 10 mg

Boehringer Ingelheim		28 Mar 2019
BI Trial No.: 1346.9		
Doc. No.: c03559983-04	Trial Protocol	Page 67 of 116

PoCC is established if at least one model is statistically significant, rejecting the null hypothesis of a flat dose response relation over 12 weeks for the primary endpoint (mean change from baseline in composite MCCB score) jointly for each of the candidate dose response models with a contrast test controlled for the family-wise type I error rate at one-sided $\alpha = 0.05$.

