If PoCC is established, the best-fitting model(s) from the above set of six models can be refitted to the data without any parameter assumptions to generate new estimates of the model parameters from the data. The final model will be obtained via weighted model averaging across the significant models based on the Akaike Information Criterion (AIC) (the smaller the AIC value the better the model fit). The target dose(s) can then be determined from that model by incorporating information on the minimum clinically relevant effect as well as safety information. The target dose should be chosen within the dose range investigated (0mg-25mg) though the actual modelling will be performed on a broader range of doses including extrapolation.

Figure 7.3.1.1: 1 Shape of the dose response patterns considered plausible in the MCPMod

Page 68 of 116

Proprietary confidential information © 2019 Boehringer Ingelheim International GmbH or one or more of its affiliated companies

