7.6 RANDOMIZATION

Eligible patients will be randomized with ratio of 1:1:1:1:2 to BI 425809 2 mg, 5 mg, 10 mg 25 mg and placebo. The randomization will be implemented in blocks to achieve balanced allocation to each treatment arm. In addition, randomization will be stratified for the main study alone and for the main study and the imaging substudy, i.e., patients who give consent to participate in the imaging substudy besides the main study will be randomized with the same ratio of 1:1:1:1:2 to the five treatment arms as for those who consent to the main study but do not consent to participate in the imaging substudy. When the total sample size for the main study is achieved, the randomization to the stratum of the imaging sub-study will stop.

The randomization will be conducted via an interactive response technology (IRT). BI will arrange for the randomization and the packaging and labelling of trial medication. The randomization list will be generated using a validated system, which involves a pseudo-random number generator so that the resulting treatment will be both reproducible and non-predictable. The block size will be documented in the CTR. Access to the codes will be controlled and documented.

7.7 **DETERMINATION OF SAMPLE SIZE**

For the purposes of calculating the sample size for this phase II trial, we consider a range of standardized effect sizes showing better efficacy of BI 425809 as compared to placebo in the composite MCCB score change from baseline after 12 weeks of treatment, i.e., 0.3, 0.35, 0.4 and 0.45, and assume the six candidate dose response patterns as described in Section 7.3.1.1. Since the randomization allocation ratio for the four BI 425809 dose arms and placebo is 1:1:1:1:2, the sample size required for the placebo arm and the active treatment arms are displayed separately. Table 7.7: 1 below gives the sample size calculations under different effect sizes using 1-sided type I error rate of 0.05 and 80% power. The sample size calculations are performed using the MCPMod approach assuming the six plausible dose response patterns as described in Section 7.3.1.1 and implemented using the statistical software R package 'DoseFinding' (R15-2001) version 0.9-12 released on 28 SEP 2014 (depends on R version $\geq 2.15.0$). The R codes for the sample size calculations as well as the analyses using the MCPMod approach will be provided in the TSAP.

Table 7.7:1	Sample size calculation under different effect sizes for the composite

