	MCCB score change from baseline with 80% power and one-sided
	alpha of 0.05

Standardized Effect size	0.3	0.35	0.4	0.45
Power = 80%				
N for Placebo	204	150	116	92
N for each active treatment arm	102	75	58	46
Total	612	450	348	276
Adjusting for 10% dropout				
N for Placebo	228	168	130	104
N for each active treatment arm	114	84	65	52
Total	684	504	390	312

A sample size of 75 evaluable patients in each of the BI 425809 arm and 150 evaluable patients in the placebo arm is needed to establish PoCC of a standardized effect size of 0.35 with an average power of 80% and one-sided alpha of 0.05. Assuming a 10% dropout rate which is considered reasonable based on CIAS trials to date, 84 patients in each of the BI 425809 arm and 168 patients in the placebo arm are required. Therefore a total sample size of 504 evaluable patients with 84 patients in each of the BI 426809 arm and 168 patients in the placebo arm is chosen for this phase II trial.

The sample size calculations in Table 7.7: 2 consider a range of effect size and power for a direct comparison between BI 425809 doses and the placebo. Two-sample t-test is used for these exploratory treatment comparisons without adjusting for multiplicity.

Table 7.7: 2Sample size calculations under different effect sizes and power for the
composite MCCB score change from baseline with one-sided alpha of
0.05

Effect size	0.3	0.35	0.4	0.45	0.5	0.55
Power = 85%						
N for each active treatment arm	151	111	85	68	55	46
N for Placebo	302	222	170	136	110	92
Total sample size adjusting for 10% dropout	1008	744	570	456	372	312
Power = 80%						
N for each active treatment arm	132	97	75	59	48	40
N for Placebo	264	194	150	118	96	80
Total sample size adjusting for 10% dropout	882	648	504	396	324	270
Power = 75%						
N for each treatment arm	117	86	66	53	43	36
N for Placebo	234	172	132	106	86	72
Total sample size adjusting for 10% dropout	780	576	444	354	288	240

The two-sample t-test method with unequal n's in nQuery Advisor® 6.1 statistical package by Statistical Solutions Ltd is used for the sample size calculations.

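### Does the SAP's 0.35 target-dose threshold need a named SD, a stated rationale and a rule for when no dose reaches it?

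*SAP*

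**What the plan says.** SAP 7.4.1 holds the only numeric target-dose rule in the visible text: "Estimate of the target dose is the smallest dose producing an effect greater than or equal to the target effect size of 0.35". The effect is read from the AIC-weighted average of the refitted models, and safety and other relevant information are weighed alongside it. The same section states the input to that curve: "The change from baseline in MCCB overall composite t-score at Week 12 as well as the corresponding variance-covariance matrix are estimated", using an MMRM. The fitted curve is therefore in T-score points.

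Protocol 7.3.1.1 says that, for sample size, "the maximum standardized effect size is assumed to be 0.35". On the candidate shapes it adds: "Except in the beta model, the maximum effect is assumed to be achieved at the maximum dose being tested". The beta model peaks at 10 mg. The protocol then says the target dose is determined "by incorporating information on the minimum clinically relevant effect as well as safety information", gives no value for that effect, and confines the dose to 0-25 mg although the modelling itself may extrapolate.

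Protocol 7.7 states that 75 evaluable patients per active arm and 150 on placebo "is needed to establish PoCC of a standardized effect size of 0.35", with average power 80% at one-sided alpha 0.05. It also promises that R code for the sample size and "the analyses using the MCPMod approach will be provided in the TSAP".

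**The concern.** Dose finding is part of the primary objective, and this one sentence turns the fitted curve into a dose. Three things look unsettled.

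- **Status of the number.** A planning maximum and a minimum clinically relevant effect are different quantities. The SAP uses the planning maximum as the threshold without saying that the two coincide.
- **Scale.** The curve is in T-score points and 0.35 carries no unit. If the SD of change were 5-10 points (not in the documents), 0.35 raw points would be only 0.35/10 = 0.035 to 0.35/5 = 0.07 SD, and almost any rising curve would qualify at a very low dose. Even on the standardised reading, the SD is not named.
- **No stated output if the threshold is unmet.** The test can succeed while the averaged curve stays below 0.35 SD across 0-25 mg. No interval for a returned dose is described either.

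If these points were settled only after unblinding, the reported target dose could depend on choices made with the results in view.

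**Working it through.** **1. The plan's own figure.** Inputs: six shapes from the contrast table in SAP 7.4.1, 75/150 evaluable patients, maximum 0.35 SD, one-sided alpha 0.05 (Protocol 7.7). The maximum-contrast critical value (multivariate t, 445 df) is 2.07. Power by shape:

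- linear 75.6%
- linear in log 82.8%
- Emax 81.5%
- sigmoid Emax 85.8%
- logistic 80.0%
- beta 84.8%

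The mean is 490.5/6 = 81.8%, against the stated 80%. Dropout: 75/0.9 = 83.3, rounded up to 84 per active arm; placebo 2 x 84 = 168; total 4 x 84 + 168 = 504. The design reproduces, and 0.35 enters it in SD units.

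**2. The unit.** SAP 7.4.1 refers to Protocol 7.3.1 and 7.7 for the design stage. In Protocol 7.7 the title of Table 7.7: 1 speaks of effect sizes and its row label says standardised effect size; Table 7.7: 2 says only effect size. The terms are interchangeable there. An effect size of 0.35 in the SAP is the same standardised quantity.

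**3. Which SD.** Protocol 7.7 standardises the change from baseline in the composite score. With equal variances s² at baseline and Week 12 and correlation r:

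- SD of change = s·sqrt(2(1 - r))
- baseline-adjusted Week 12 SD = s·sqrt(1 - r²)
- ratio = sqrt(2/(1 + r)) = 1.08 at r = 0.7 and 1.03 at r = 0.9

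On the adjusted scale, the choice moves the threshold from 0.35 to at most 0.35 x 1.08 = 0.38 SD. A larger ratio, 1/sqrt(1 - r²) = 1.40 to 2.29, arises only with the SD of the score itself, which Protocol 7.7 does not use. The values of r are assumptions.

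**4. Can the test succeed with the threshold unmet?** Yes. Take data lying exactly on the linear shape, (0, 0.08, 0.2, 0.4, 1) at (0, 2, 5, 10, 25) mg.

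- Weighted mean = 75 x 1.68/450 = 0.28
- Weighted sum of squares = 75 x 1.2064 - 450 x 0.28² = 90.48 - 35.28 = 55.20
- Test statistic = (maximum effect) x sqrt(55.20) = 7.43 x (maximum effect)

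It reaches 2.07 at a maximum effect of 0.28 SD, below 0.35. Over the six shapes this point lies at about 0.24-0.28 SD.

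**5. How often.** Simulation: 20,000 trials per shape, 75/150 complete cases, known SD, AIC averaging over significant models, threshold 0.35 SD on a 0-25 mg grid. Share of trials with established proof of concept that return no dose, as a range over shapes:

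- true maximum 0.30 SD: 42-46% (54-58% return a dose)
- true maximum 0.35 SD: 31-36%
- true maximum 0.40 SD: 21-25%
- true maximum 0.45 SD: 12-17%

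At a true maximum of 0.35 SD, the median returned dose is 11-18 mg for the five shapes whose true answer is 25 mg. An estimate capped at 25 mg can only err downwards when the truth sits at the cap, so much of that shift is built in.

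**6. What these shares measure.** The simulation already fixes the unit, the SD and the not-reached output. Rewriting the sentence to state all three would leave every share as it is. They show how often the not-reached result would arise. They do not measure harm from the missing words.

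**The case for a change.** The best case for a change is that the omitted branch is common. Under the sponsor's own planning assumption, about one successful trial in three would return no dose. Stating the unit, the SD, the reason for 0.35 and the not-reached output would take one paragraph before unblinding, with no new data and no effect on the test. An interval for the returned dose would also help: with a true maximum of 0.45 SD under Emax, the true dose is 11.5 mg and the 10th to 90th percentile of estimates is about 4-20 mg.

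What stands is that the visible sentence is terse, that the interval would be useful in reporting, and that the dose estimate is imprecise at this sample size. The rest carries less weight. The not-reached case needs no new rule, because the existing one then selects nothing and the dose-response profile is still estimated. SAP 7.4.1 mirrors the protocol's sentence, putting 0.35 where the protocol left the clinically relevant effect without a value. Powering a trial on the effect one hopes to target is a defensible choice, and whether the two should be equal is a matter of judgement. Finally, the R code promised in Protocol 7.7 is not in the public copy, nor is SAP Section 9, which the history table lists as revised. The conversion or fallback may be there, so its absence from the plan cannot be shown.

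**Conclusion.** No change is needed. The visible text does leave the SD, the clinical status of 0.35 and the not-reached output unstated, but an analyst following it would multiply 0.35 by an SD for change from baseline and report that no dose in 0-25 mg reached it if that happened. The remaining ambiguity of scale is about 3-8%, assuming a baseline to Week 12 correlation of 0.7-0.9 and equal variances. The 31-36% no-dose share at a true maximum of 0.35 SD reflects limited precision at 75/150 patients, under assumed model bounds, complete data and a known SD; wording would not reduce it. An interval for the target dose is a desirable addition to the report, and its absence contradicts nothing in the plan. Because the dose choice also weighs safety and other information, the threshold is one input among several. The proof-of-concept test, its error control and its power do not depend on this sentence.
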